8. STUDY METHODS

8.1. Study design

8.1.1. Design and study procedures

This study is a prospective, multicenter, non-interventional study to evaluate the efficacy of etanercept in patients with RA, PsA, axSpA or PsO.

Efficacy data will be documented within a period of 12 months and health outcomes every quarter in the course of routine treatment. An overview of the documentation to be performed can be found in Table 1 below.

Table 1: Overview of study procedures					
	Visit 1 Week 0	Visit 2 Week 12	Visit 3 Week 24	Visit 4 Week 36	Visit 5 Week 52
Medical history	X				
Inflammation in MRI (axSpA)	X				
Radiological Sacroiliitis (axSpA)	X				
Participation in the “Together” program	X				
Inclusion/exclusion criteria	X				
Treatment/medications					
Prior treatment	X				
Treatment with Enbrel	X	X	X	X	X
Concomitant treatment		X	X	X	X
Safety parameters					
Physical examination	X				
Laboratory	X	X	X	X	X
AE documentation		X	X	X	X
Efficacy					
Examination of joints	X	X	X	X	X
PASI (PsO)	X	X	X	X	X
Morning stiffness (RA, axSpA, PsA)	X	X	X	X	X
Patient and physician global assessment	X	X	X	X	X
Pain	X	X	X	X	X
Fatigue	X	X	X	X	X
Occiput-to-wall distance (axSpA)	X	X	X	X	X
Dactylitis (PsA)	X	X	X	X	X
Nail involvement (PsO, PsA)	X	X	X	X	X
Enthesitis (PsA, axSpA)	X	X	X	X	X
Pruritus (PsO)	X	X	X	X	X
Health outcomes					
FFbH (RA, axSpA, PsA)	X	X	X	X	X
BASDAI (axSpA)	X	X	X	X	X

DLQI (PsO)	X	X	X	X	X
PHQ-2	X	X	X	X	X

8.1.2. Primary study end points

- Patients with RA: Proportion of patients who attain the desired treatment goals (see Table 2) at the week 12 and week 24 time points under monotherapy or in combination with MTX and maintain these long-term over a period of 52 weeks.
- Other indications: Proportion of patients who attain the desired treatment goals according to guidelines (see Table 2) in each respective indication at the week 12 and week 24 time points.

8.1.3. Secondary end points at weeks 12, 24, 36, and 52

All patients:

- Proportion of patients who continue treatment with etanercept,
- Occurrence of adverse events,
- Remission,
- Patient global assessment,
- Fatigue,
- Pain (VAS),
- Physician global assessment,
- PHQ-2
- Comparison of the parameters “patient global assessment,” “fatigue,” “pain,” “physician global assessment,” and “PHQ-2 across all indications,
- Comparison of FFbH and morning stiffness among patients with RA, axSpA, and PsA,
- Discontinuation of treatment due to a lack of efficacy or adverse events,
- Nature of further treatment if treatment has been discontinued,

Additionally for RA patients:

- FFbH
- CDAI
- SDAI

Additionally for axSpA patients:

- BASDAI,
- FFbH
- Enthesitis
- Occiput-to-wall distance

Additionally for PsA patients:

- BSA

- Dactylitis
- Enthesitis
- FFbH

Additionally for PsO patients:

- PASI, median time to PASI75, body segment (head, trunk, upper and lower extremities) and component-related subscales (erythema, induration, flaking) over 24 weeks,
- DLQI,
- Pruritus
- BSA.

The following indication-related laboratory tests will be documented if they are available as part of a routine assessment:

- Erythrocyte sedimentation rate (ESR), C-reactive protein (CRP)

In addition, the following laboratory tests will be documented for patients with RA, PsA, and axSpA if they are available as part of a routine assessment:

- Rheumatoid factor (RF) and anti-CCP antibodies.
- HLA-B27 at Visit 1 (just axSpA).

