Title	
- ADEQUATE STUDY -
 
A prospective, multicenter non-interventional study to evaluate the efficacy of Enbrel® (etanercept) over a period of 12 months in the routine treatment of patients with rheumatoid arthritis, axial spondyloarthritis, psoriatic arthritis, or plaque psoriasis with particular focus on the clinical status improvements still observable after 12 weeks of treatment.

Study number:	B1801385
Version:	Final 1.3
Date:	30.01.2015
Name of active substance:	Enbrel® (etanercept)
Scientific question and goals	
The goal of this non-interventional study is to evaluate the efficacy of etanercept during routine clinical use over a maximum of 12 months in patients with rheumatoid arthritis, psoriatic arthritis, axial spondyloarthritis, or plaque psoriasis. In so doing, particular attention will be paid to the proportion of those patients who only attain the desired treatment goal after 12 weeks of treatment. The primary efficacy end point for the study is the proportion of patients who attain the desired treatment goal after 12 and 24 weeks, whereby data collection tools including DAS28, PASI, PGA, and ASDAS will be used to define the indication-specific treatment goal in accordance with the currently valid national/international treatment guidelines and -recommendations.
 
The secondary efficacy end points for the study include not only objective measures of disease activity but also patient-reported

	
information regarding function.
 
Safety and tolerability of the treatment are recorded based on the documentation of adverse events and the reasons for premature ending of treatment.

Author	[name] Pharma GmbH [name]

TABLE OF CONTENTS

TABLE OF CONTENTS	3
1. LIST OF ABBREVIATIONS	5
2. RESPONSIBILITIES	7
3. ABSTRACT	7
4. AMENDMENTS AND UPDATES	7
5. MILESTONES	7
6. RATIONALE AND BACKGROUND INFORMATION	8
6.1. Background information	8
6.2. Study rationale	8
7. SCIENTIFIC QUESTION AND GOALS	10
8. STUDY METHODS	10
8.1. Study design	10
8.1.1. Design and study procedures	10
8.1.2. Primary study end points	12
8.1.3. Secondary end points at weeks 12, 24, 36, and 52	12
8.2. Study setting	13
8.2.1. Study conduct	13
8.2.2. Inclusion criteria	14
8.2.3. Exclusion criteria	14
8.3. Variable description	14
8.4. Source documents	16
8.5. Calculation of case numbers	16
8.6. Data management	17
8.7. Data analysis	17
8.8. Quality control	17
8.9. Strengths and limitations of the study methodology used	18

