6.2. Study rationale

Approx. 20 - 30 % of patients end their treatment with etanercept during the first year of treatment, whereby the discontinuation of treatment is due to a lack of efficacy or side effects. The German and also the EULAR guidelines for the treatment of RA recommend a change of treatment after 3 and at most after 6 months if the criterion for low disease activity has not been attained [4, 11, 12]. The treatment guidelines for the other indications for which etanercept is approved are similar.

Clinical studies in the indications of RA, axSpA, PsA, and PsO show that it may be worth continuing treatment beyond a period of 12 weeks even if the criterion for low disease activity has not yet been attained, because the number of patients who only attain this criterion beyond the 12 weeks is increasing.

In routine care, according to national and EULAR guidelines, the medical assessment of the treating rheumatologist or dermatologist and other criteria should be taken into consideration in addition to the purely numerical assessment of treatment goals. Therefore, the assessment as to whether the treatment goals were ultimately attained depends in everyday clinical practice not only on the numerical results from the DAS, ASDAS (or PSARC) or PASI tools, but also on the overall evaluation of the physician and the patient, as well as on the treatment outcomes reported by the patient ("patient reported outcomes," PRO), treatment satisfaction, and other social and functional factors.

In summary, it is therefore the primary goal of this study to check how many patients in everyday clinical practice benefit from the continuation of treatment with etanercept beyond 12 weeks, even if the defined treatment goal has not yet formally been attained at that time but treatment is continued based on the judgment of the prescribing physician and the patient. In so doing, this rate is to be compared across the different indications. The variables which also reflect compliance with the treatment guidelines by physicians are to be examined in terms of additional influencing factors such as disease duration, concomitant medications, or PROs.

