Early treatment with biologics is recommended for all indications in order to attain improved quality of life and patient function and to exert a favorable effect on comorbidities, e.g. cardiovascular diseases. It is not yet known whether the burden of disease is comparable in the different indications at the start of treatment with etanercept. Here, a better understanding of these relationships could help doctors to determine the optimal time point for the start of treatment with etanercept.

In this study, the variables are examined in a joint study setting (as far as is currently known, for the first time), which permits these variables to be compared directly across the different indications. Even though the treatment goals and the extent of disease activity in the different indications are determined based on different tools, it will still be possible to measure and compare PROs in particular, such as global assessment, pain, fatigue, mental health and - at least for the rheumatological indications - FFbH (comparable with the HAQ) and morning stiffness, regardless of the indication. The overall physician's assessment will also be measured in all indications and compared between the individual indications.

In addition to findings regarding relevance to practice and the reality of care according to treatment guidelines and recommendations, patient compliance with the treatment plan will be scientifically studied in detail.

The goal of Pfizer's own "TOGETHER" program is to improve patient treatment compliance with training measures. This study is to investigate the extent to which participation in the "TOGETHER" program influences treatment compliance.

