7. SCIENTIFIC QUESTION AND GOALS

The primary goal of this study is to determine how many patients treated under everyday conditions benefit from the continuation of treatment with etanercept beyond 12 weeks even if the desired treatment goal (see Table 2) has not yet been attained at that time point, as well as to compare these rates across the different indications. For this purpose, the following questions are to be answered based on a reliable data body collected during clinical routine:

- Proportion of patients who have not attained defined treatment goals for each respective indication after 12 weeks, but do attain these between weeks 12 and 24.
- Proportion of patients who have attained the desired treatment goal after 12 weeks,
- Proportion of patients who continue treatment up to week 52 in the different indications,
- Comparison of PRO results across indications,
- How is the decision made in everyday clinical practice whether treatment with etanercept is continued or discontinued (i.e. which other parameters are taken into consideration, for example PRO or physician's global assessment),
- At what time point is the decision made to switch treatment (i.e. after 3 or 6 months, or even later),
- Are there predictive factors for the continuation of treatment with etanercept,
- What factors may influence treatment compliance (e.g. participation of the patients in a compliance program).

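### The primary end point in 8.1.2 does not measure late attainment, which sections 6.2 and 7 make the primary goal, and its 52-week clause for RA does not match the title page or the sizing in 8.5

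*Combined protocol and SAP*

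**What the plan says.** **The goal.** Section 6.2 asks how many patients benefit from going on past week 12 when the goal "has not yet formally been attained at that time but treatment is continued based on the judgment of the prescribing physician and the patient", and adds that "this rate is to be compared across the different indications". Section 7 repeats this and puts first, among the questions to be answered, the proportion "who have not attained defined treatment goals for each respective indication after 12 weeks, but do attain these between weeks 12 and 24". The title page says that "particular attention will be paid to the proportion of those patients who only attain the desired treatment goal after 12 weeks of treatment".

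**The end point.** The title page gives the primary efficacy end point as "the proportion of patients who attain the desired treatment goal after 12 and 24 weeks". Section 8.1.2 has, for RA, the "Proportion of patients who attain the desired treatment goals (see Table 2) at the week 12 and week 24 time points", on monotherapy or with MTX, "and maintain these long-term over a period of 52 weeks". For the other indications it has attainment at the same two time points without the maintenance condition. The secondary list in 8.1.3 has no late-response proportion. The nearest entries are remission at each visit and, for psoriasis, median time to PASI75. Its cross-indication comparisons concern patient and physician global assessment, fatigue, pain, PHQ-2, FFbH and morning stiffness.

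**The analysis.** Section 8.5 sizes RA on adequate response after 12 weeks (74% on ETN+MTX, 66% on monotherapy; 800 and 400 patients) and allows an optional GEE. Section 8.7 provides frequencies and one logistic regression for the two RA treatment subgroups. It leaves detail to a separate SAP but requires a protocol amendment for any substantial change to the primary end point.

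**The concern.** The goal is about a transition: off goal at week 12, on goal by week 24. The end point is about status at two visits. A team following 8.1.2 and 8.7 to the letter could report the primary end point in full and still not answer the primary question.

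The denominator is also open. Section 6.2 describes patients who continue treatment. The first question in section 7 does not say whether the base is all patients, all non-attainers, or non-attainers who continue. Section 11.1 plans four interim analyses with conference abstracts, so without a written definition the denominator and the handling of patients who stop could be chosen with results in view.

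The 52-week clause applies to RA only. If it is part of the end point, RA and the other indications are not measured alike, although comparing them is part of the goal, and the RA result depends on whether the clause is applied.

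**Working it through.** **1. The plan's own sample size.** Inputs from 8.5: 0.74 (n = 800) against 0.66 (n = 400), two-sided 5%, 80% power.
- Odds ratio = (0.66/0.34)/(0.74/0.26) = 0.682, as stated.
- The two-proportion formula with continuity correction gives 400 + 800 = 1200, an exact match; without the correction it gives 1146.
- Power at 800/400, uncorrected: pooled rate 0.7133; standard error 0.02769 under the null and 0.02831 under the alternative; (0.08 − 1.96 × 0.02769)/0.02831 = 0.909, so power is 81.8%. With the correction it is 80.0%.

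The arithmetic is right, but it powers an MTX contrast at week 12 and not the late-response question.

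**2. The two readings of 8.1.2.** Let p12 and p24 be the proportions at goal, and L the share of week-12 attainers who lose the goal by week 24. The documents give no L, so 0 to 30% is assumed.
- *At goal at both visits:* success = p12 × (1 − L). Anyone off goal at week 12 is a failure whatever happens later.
- *Two separate rates:* late responders as a share of all patients = p24 − p12 × (1 − L); as a share of non-attainers, divide by (1 − p12). The answer depends on L, which the two rates do not reveal.

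With the psoriasis rates cited in 6.1 (PASI75 standing in for the Table 2 goal):

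| Rates at weeks 12, 24 | L | Late, of all patients | Late, of non-attainers | At goal at both visits |
|---|---|---|---|---|
| 37.2%, 59.9% (once weekly) | 0 | 22.7% | 36.1% | 37.2% |
| 37.2%, 59.9% (once weekly) | 0.3 | 33.9% | 53.9% | 26.0% |
| 62.4%, 78.2% (twice weekly) | 0 | 15.8% | 42.0% | 62.4% |
| 62.4%, 78.2% (twice weekly) | 0.3 | 34.5% | 91.8% | 43.7% |

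**3. Precision available for late response.** Maximum 95% half-width = 1.96 × √(0.25/n), before attrition.
- RA, 8.5 rates: non-attainers = 800 × 0.26 + 400 × 0.34 = 344, giving ±5.3 points.
- RA, remission rate from 6.1 with the 40% increase read as relative: p12 = 0.50/1.4 = 35.7%; non-attainers = 1200 × 0.643 = 771, giving ±3.5.
- Psoriasis: 300 × 0.628 = 188, giving ±7.1; 300 × 0.376 = 113, giving ±9.2.
- RA minus psoriasis, at most 1.96 × √(0.25/n1 + 0.25/n2): from ±8.0 (771 and 188) to ±10.6 (344 and 113).

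The documents give no rates for axSpA or PsA.

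**4. The RA definition behind 8.5.** The 74% and 66% are adequate-response rates built on DAS28 plus global assessments; the RA goal in Table 2 is DAS28 <2.6. Holding the odds ratio at 0.682 with overall remission at 35.7%, the rates are 38.6% and 30.0% ((800 × 0.386 + 400 × 0.300)/1200 = 0.357). Power is then (0.0859 − 1.96 × 0.02934)/0.02865 = 0.990, or about 84%. The stated 80% therefore belongs to the 8.5 rates only.

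**5. RA wording side by side.** Title page: weeks 12 and 24. Section 8.1.2: weeks 12 and 24, maintained over 52 weeks. Section 8.5: week 12, adequate response. Section 8.7: the end point by name, with no time point.

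**The case against.** The strongest reply is that the protocol already commits to the quantity. Section 7 lists it first among the questions to be answered, Visits 2 and 3 give paired data on each patient, and the SAP was still to come. That stands, and it rules out a stronger reading that a reader might infer: that the study cannot identify late response. It can, by counting transitions. The ranges above show what would be lost if only the two rates were reported, and their width comes from an assumed loss rate. What remains is that late response has no end point status and no specified analysis, and by 8.7's own rule a substantial change to the primary end point needs a protocol amendment, so the SAP alone would not settle it.

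A reader might also count four rival RA end points. The documents do not support that: silence on time point in 8.7 is not a competing definition, and 8.5 may simply have chosen week 12 for sizing. The real conflict is the 52-week clause, together with the different response definition in 8.5.

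The 6.1 remission figures could be read as 10% rising to 50%, but an increase stated against the week-12 status is most naturally relative, so that reading is not used here.

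Median time to PASI75 bears on late response, but only in psoriasis and only for one criterion of the goal. It is also fair that the study is non-interventional and claims no proof of efficacy (8.9). That is why the remedy is estimation and not another test.

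**Conclusion.** The point holds. On neither reading does the 8.1.2 end point measure the goal set in 6.2 and 7, and the only inferential analysis specified for the primary end point is an RA treatment contrast sized on week-12 response. If only the two rates were reported, the once-weekly psoriasis figures would fit late response in 36% to 54% of non-attainers, assuming that 0 to 30% of week-12 attainers lose the goal and that PASI75 stands for the goal. On the joint reading, the 23% to 34% of all patients who respond late would be failures.

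Separately, the RA end point includes 52-week maintenance in 8.1.2 but not on the title page, and 8.5 sizes on a different response definition at week 12. The sample-size arithmetic is not in error, but its power statement applies only to the adequate-response rates. The collected data can answer the primary question; the plan does not yet say how.

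**What to change.** By protocol amendment:

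1. Add late response, per indication, to the primary end points in 8.1.2 and to 8.7. Among patients with known week-12 status who are not at goal and continue etanercept, report the proportion at goal at week 24 with a 95% CI. Count those who stop before week 24 as not attained. Because section 7 speaks of attainment between the two visits, add a sensitivity analysis that counts any attainment documented in that interval before stopping. Report unknown week-12 or week-24 status separately; this matters because 8.1.3 documents ESR and CRP only when routinely available. Also show late response as a share of all patients, the number of non-attainers who stop at week 12, and the number at goal at week 12 who lose it by week 24.
2. Report between-indication differences with 95% CIs as descriptive, noting, as 6.2 does, that "the treatment goals and the extent of disease activity in the different indications are determined based on different tools".
3. List week-12 attainment, week-24 attainment and maintenance to week 52 as separate end points, align the title page, and state in 8.5 and 8.7 which of them, at which time point, the MTX logistic regression tests.
4. State in 8.5 that 74% and 66% are adequate-response rates and not DAS28 <2.6 rates, so that the 80% power holds for those rates only, and give the late-response precision as the range in step 3 of the working, before attrition.

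The cost is an amendment and a few tables, with no added patients or visits. The trade-off is that late response is estimated, not tested.

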8.2. Study setting

8.2.1. Study conduct

The planned recruitment period is 18 months. With a planned observation duration of 12 months per patient, the entire study would thus last for 30 months. The study is to start in Q1/2015 and will be ended in Q3/2017. In all, about 2100 patients in 300 centers are to be included in this non-interventional study, of whom about 1200 will have a diagnosis of RA and about 300 each will have a diagnosis of axSpA, PsA, and PsO.

After regular initiation on treatment with etanercept, patients will be documented for a period of up to 12 months. In accordance with section 67, paragraph 6 of the AMG, notice of the conduct of the study will be made to the National Association of Statutory Health Insurance Physicians, the Central Federal Association of Health Insurance Funds, and the competent central federal authority. Logistics, database creation, data input, and evaluation and reporting will be performed by a CRO Winicker Norimed.

Due to the high number of participating centers and patients throughout Germany, it is expected that the results from the study will have a representative nature. Another advantage of the study design lies in the fact that the 4 different indications will be examined within one study setting, which should improve the comparability of the study results across indications.

8.2.2. Inclusion criteria

Patient eligibility should be checked and documented by the treating physician before patients are included in the study. The decision to commence treatment with etanercept shall be made in advance and independently of any participation in this study.

Proof of a personally signed and dated informed consent form stating that the patient (or legal representative, if applicable) has been informed of all concrete aspects of the study is a prerequisite for inclusion in this study.

Patients eligible for documentation must meet the following criteria,:;

1. Confirmed diagnosis of RA, axSpA, PsA or PsO,
2. No prior treatment with etanercept and eligibility for treatment with etanercept according to the summary of product characteristics,
3. Patient age ≥ 18 years,

8.2.3. Exclusion criteria

The contraindications, special warnings, and precautions according to the summary of product characteristics for etanercept shall apply. The additional documentation of the patient in another post-marketing study with etanercept is not permitted.

8.3. Variable description

The primary and secondary end points are listed in section 8.1.2 and section 8.1.3.

All of the indication-specific efficacy measures used in this study, such as DAS28, BASDAI or PASI, are clearly defined and meet the current international scientific standard. The definitions for “desired treatment goals” in the individual indications were based on recommendations, including from national and international treatment guidelines. An overview of these recommendations can be found in Table 2 below.

Table 2: Overview of desired treatment goals and minimum efficacy criteria in the different approved etanercept indications, based on the current latest treatment guidelines

Indication	Desired treatment goal	Minimum efficacy	Source
PsO	
 • PASI75 or • PGA (“clear” or “almost clear”) and • DLQI 0 or 1 	
 • PASI50 and • DLQI <5 or improvement of at least 5 points 	S3 Guidelines for the systemic treatment of PsO [7, 8]
RA	
 • DAS28 <2.6 	
 • DAS28 \leq3.2 or • Physician assessment, e.g. based on radiology findings 	S1 Guidelines of the DGRh [4]
axSpA	
 • ASDAS <1.3 	
 • BASDAI: 50% relative difference or absolute difference of 2 points (scale from 0 -10) and • Expert opinion on continuation: yes/no 	Kiltz et al. 2014 [13]
PsA	
 • DAS28 <2.6 or • MDA criteria met^a 	
 • DAS28 \leq3.2 or • Physician assessment, e.g. based on radiology findings 	a) Mease 2011 [5]

Selected parameters, such as remission, low disease activity, or continuation of treatment, will be analyzed for potential influencing variables (e.g. duration of disease, clinical outcomes, PRO).

Detailed information on the calculation of variables and on data evaluation in general will be set forth in a separate statistical analysis plan (SAP) before the start of the evaluation.

